#### **4.2.2.2 Coding of Adverse Event Terms**

The AE term (Investigator term) will be assigned to the lowest level term (LLT), and a preferred term (PT) will be classified by a system organ class (SOC) according to the Medical Dictionary for Regulatory Activities (MedDRA) thesaurus, Version 20.

Although there can be multiple SOCs for a PT, each PT will be linked with one SOC, namely the primary SOC which is automatically assigned by MedDRA.

The following coding data will be presented:

- LLT
- PT
- SOC

Coding of AEs will be provided by data management at PSR in a coding spreadsheet alongside the coding of CMs and MH. The AE coding data will be merged onto the raw AE data by Subject ID and AE number. The final version of this spreadsheet will be provided prior to database lock.

In the event that no coding information is available for a specific AE, the AE will be presented as an 'Uncodable Event' in all summary tables.

AEs will be reported on a per-patient basis. On a per-patient basis this means that even if a patient reported the same event repeatedly (i.e., events mapped to the same PT) during the study period, the event will be counted only once. In the latter case the event will be assigned the worst severity and the strongest relationship to the study medication. The earliest date will be regarded as start date of the event and the latest date/time will be regarded as stop date of the event within the assigned study period.

#### 4.2.3 Clinical Laboratory Evaluations

Laboratory evaluations were performed at Presentation of attack and Day 28 in accordance with the Schedule of Study Events (Section 2.4). Blood and urine samples were collected and analyzed by local laboratory.

Table 5 presents the quantitative and qualitative laboratory tests that were performed.

**Table 5 Laboratory Tests**

Laboratory Test (Unit)
Hematology
Erythrocyte sedimentation rate (ESR) (mm/hr)
Hemoglobin (g/L)
Hematocrit (%)
Red blood cell count (RBC) ( $10^{12}/L$ )
Mean corpuscular volume (MCV) (fl)
Mean corpuscular hemoglobin (MCH) (pg)
Mean corpuscular hemoglobin concentration (MCHC) (g/L)
Total white blood cell count (WBC) ( $\times 10^9/L$ )
Platelet count ( $\times 10^9/L$ )
Differential WBC units
Neutrophils ( $\times 10^9/L$ )
Lymphocytes ( $\times 10^9/L$ )
Monocytes ( $\times 10^9/L$ )
Eosinophils ( $\times 10^9/L$ )
Basophils ( $\times 10^9/L$ )
Biochemistry
Sodium (mmol/L)
Potassium (mmol/L)
Chloride (mmol/L)
Calcium (mmol/L)
Inorganic phosphate (mmol/L)
Total protein (g/L)
Albumin (mg/L)
Glucose (mmol/L)
Creatinine ( $\mu\text{mol}/L$ )
Aspartate aminotransferase (AST) (U/L)
Alanine aminotransferase (ALT) (U/L)
Lactate dehydrogenase (LDH) ( $\mu\text{kat}/L$ )
Blood urea nitrogen (mmol/L)
Bilirubin (Total) ( $\mu\text{mol}/L$ )
Alkaline phosphatase (U/L)
Gamma-GT (U/L)
Uric acid (mg/dL)
Total cholesterol (mmol/L)
HDL cholesterol (mmol/L)
Triglycerides (mmol/L)
C-Reactive Protein (CRP) (mg/L)

Amylase (U/L)
Urine Pregnancy Test

For the quantitative laboratory parameters, if a re-test was performed at any visit, the result from the re-test for the specific visit will be used in all analyses. For the qualitative laboratory parameters, if a re-test was performed at any visit, the results of the test performed at the re-test will be used.

For each laboratory test (quantitative and qualitative), the Baseline value is defined as the last non-missing measurement collected/derived prior to the first study medication administration at 0 minutes.

For the quantitative laboratory test, the change from Baseline value at Day 28 will be calculated as the difference between the measurements obtained at Day 28 and the Baseline value.

Quantitative test results at each visit will be categorized by the laboratory as 'Normal' (within the reference range) or 'Abnormal' (outside the reference range) according to the patients' individual reference ranges provided by the analyzing laboratory (see Appendix 1). Note that Système International (SI) standardized units will have to be used alongside the individual reference ranges, so the process will be to first convert lab data to SI units and then to compare results to the individual reference ranges (also known as "normal ranges").

Abnormal results will further classified as being 'Low' or 'High' depending on whether the result is below or above the reference range limits. For all abnormal values, clinical significance (as determined by the Investigator) should be indicated.

#### **4.2.4      ECG Evaluations**

Electrocardiogram (ECG) evaluations were performed at Presentation of attack and between 30 minutes and 2 hours post infusion with study medication, in accordance with the Schedule of Study Events (Section 2.4).

Only qualitative ECG parameters were collected.

For the qualitative ECG parameters (morphology), it will be recorded whether the parameter at the specific visit was 'Normal' or 'Abnormal'. For all abnormal values, clinical significance (as determined by the Investigator) and any ECG findings should be indicated.

For each qualitative ECG parameter, the Baseline value is defined as the last non-missing measurement collected/derived prior to the first study medication administration at Presentation.

#### **4.2.5      Vital Signs Evaluations**

Vital signs evaluations were performed at Screening, Presentation of attack, 30 mins, 1, 2 and 4 hours post infusion with study medication, and Day 90, in accordance with the Schedule of Study Events (Section 2.4).

The following variables were collected:

- Height (cm) (Height was collected only at Screening).
- Weight (kg) (Weight was collected at Screening and Presentation of attack).
- Supine systolic blood pressure (SBP) (mmHg).
- Supine diastolic blood pressure (DBP) (mmHg).
- Pulse rate (bpm).
- Body temperature (°C).

For each vital signs variable, the Baseline value is defined as the last non-missing measurement collected/derived prior to the first study medication administration at Presentation.

Based on the criteria presented in Appendix 1, clinically significant vital sign measurements will be identified at each visit.

#### **4.2.6 Physical Examination**

Routine physical examination was performed at Screening, Presentation of attack, Hospital discharge, Day 28 and Day 90 in accordance with the Schedule of Study Events (Section 2.4).

### **4.3 Other Measures**

#### **4.3.1 Diagnostic Assays and IgE Testing**

Blood samples for diagnostic assays will be collected at screening. The samples will be analyzed for the following parameters: C1INH activity, C1q, C4 and C1INH auto antibodies (IgM, and IgG anti-rhC1INH).

Assays for IgE antibodies against rabbit epithelium (anti-rabbit epithelium IgE [dander]) will be performed at screening, at Day 28 after each attack, every year following screening and if AEs indicative of a hypersensitivity reaction are observed. Prior to treatment with Ruconest a negative test for anti-rabbit epithelium (dander) (cut off <0.35 kU/L) should be documented.

Similarly, assays for IgE antibodies against cow milk (anti-cow milk IgE) will be performed once at Screening.

#### **4.3.2 PK/PD Assays**

Blood samples for PK/PD assays will be collected prior to administration of the study medication for the first acute HAE attack (named Presentation), one blood sample directly following infusion (at time 5 minutes) and another blood sample between 2-4 hours post-infusion (at time 2-4 hours). The samples will be analyzed for C1INH activity (PK) and C4 (PD). C4 is additionally analyzed at Presentation of each subsequent acute HAE attack.

For the first attack, the following PK parameters will be derived, where appropriate, for C1INH activity in plasma from the concentration-time data using standard noncompartmental procedures;  $C_{max}$  and  $AUC_{0-3}$ .

#### 4.3.3 Immunogenicity

Immunology tests will be performed at Screening and for each attack at Presentation and follow-up visits Days 28 and 90 in accordance with the schedule of study events.

All patients will be tested using ELISA tests to detect for the presence of antibodies against:

- rhC1INH-specific IgG (IgG) [cut-off: >15%]
- rhC1INH-specific IgM (IgM) [cut-off: >50%]
- HRISPeluate-specific AB (HRI) [cut-off: >100%]

Plasma samples found to be above the respective cut-off level are deemed positive and are further analysed in a confirmatory displacement assay (to confirm the initial result and discriminate between specific and non-specific responses).

Three assays will be performed during the confirmatory displacement assay: displacement rAUCa, displacement rAUCb and displacement, %Difference. The value of "displacement, %Difference" is used to determine if a sample is confirmed positive for antibodies (i.e. specific antibodies are confirmed).

The following cut-off levels are used for the confirmatory displacement assay (results above cut-off are deemed positive):

- rhC1INH-specific IgG, displacement, %Difference [cut-off: ≥45% i.e. sample contains rhC1INH-specific IgG antibodies]
- rhC1INH-specific IgM, displacement, %Difference [cut-off: ≥40% i.e. sample contains rhC1INH-specific IgM antibodies]
- HRISPeluate-specific AB, displacement, %Difference [cut-off: ≥35% i.e. sample contains HRISPeluate-specific antibodies]

If specific antibodies are confirmed, a further test with a neutralizing antibody assay is performed. In other words, only samples which have been confirmed to have specific anti-rhC1INH IgG and IgM antibodies were then analyzed in the neutralizing C1INH antibody assay.

The following Neutralizing AB cut-off levels are used (results below cut-off are deemed positive):

- Neutralizing C1INH-specific AB (%) [cut-off: <64%]
- Neutralizing rhC1INH-specific AB (%) [cut-off: <54%]

Note: the original plasma sample and all corresponding confirmatory displacement and neutralizing AB assays will have the same requisition number in the QPS data file.

The anti-C1INH antibodies labels that will be used in all outputs are presented in Table 6.

**Table 6 Antibody Labels**

Antibodies	Label
Antibodies against rhC1INH-specific IgG	Anti-rhC1INH (IgG)
Antibodies against rhC1INH-specific IgM	Anti-rhC1INH (IgM)
Antibodies against HRISPeluate-specific AB	Anti-HRI
Neutralizing antibodies against C1INH-specific AB	Anti-C1INH NAb
Neutralizing antibodies against rhC1INH-specific AB	Anti-rhC1INH NAb

The actual values and whether these are above or below cut-off will be presented in the listings. Separate listings will be produced of the results of the screening ELISA and the results from the

displacement and neutralizing assays. The associated attack number and visit will be clearly shown for the results from the displacement and neutralizing assays.

#### **4.3.4 Patient Disposition**

The following data will also be presented:

- Date of Screening visit.
- Date of informed consent.
- Date and reason for withdrawal from the study, where applicable.

The analysis sets and subgroups defined in Section 3 will be analyzed and presented as part of the patient disposition data.

#### **4.3.5 Protocol Violations**

Protocol violations are defined as violations that might affect the efficacy or treatment of a patient, and lead to the exclusion of patients from the analysis sets defined in Section 3.

Protocol deviations are defined in a separate document produced by Pharming prior to database lock. Protocol deviations are determined programmatically by data management, manually during data review and identified by the monitors during site visits. All deviations identified will be added to an excel spreadsheet which shall be sent to Quanticate. Protocol violations which may lead to exclusion from the defined analysis sets will be identified at the Data Review Meeting prior to database lock.

#### **4.3.6 Demographics and Baseline Patient Characteristics**

Patient demographic data was collected on the 'Demographics' CRF page at Screening visit, which comprised of date of birth, gender, Tanner Stage, height, weight and race.

Age (in years) will be calculated relative to the Screening Visit by means of the following algorithm:

Age (Years) = Visit\_Y – Birth\_Y – (0 < Visit\_M < Birth\_M OR (Visit\_M = Birth\_M AND 0 < Visit\_D < Birth\_D)), with variables as follows:

- Birth\_Y = Year of birth.
- Birth\_M = Month of birth.
- Birth\_D = Day of birth.
- Visit\_Y = Year of Screening visit.
- Visit\_M = Month of Screening visit.
- Visit\_D = Day of Screening visit.

Missing demography data will be handled according to the rules specified in Section 5.5.2.3.

#### **4.3.7 Medical History**

Medical history contains information about conditions that a patient might have suffered from prior to the first administration of study medication at Presentation, or conditions that were on-going at the time of the first administration of study medication.

Medical history, relevant HAE history and relevant HAE attack history were collected at Screening.

Each term recorded on the medical history page will be assessed to determine whether the event was a past or present condition at Screening. This will be taken directly from the tick box on the CRF.

##### **4.3.7.1 Coding of Medical History Terms**

The medical history term (Investigator term) is assigned to the LLT, and a PT will be classified by a SOC according to the MedDRA thesaurus, Version 18 or higher, depending on the latest version available during the study.

Although there can be multiple SOCs for a PT, each PT will be linked with one SOC, namely the primary SOC which is automatically assigned by MedDRA.

The following coding data will be presented:

- LLT
- PT
- SOC

Coding of MH will be provided by data management at PSR in a coding spreadsheet alongside the coding of AEs and CMs. The MH coding data will be merged onto the raw MH data by Subject ID and MH number. The final version of this spreadsheet will be provided prior to database lock.

Medical history will be reported on a per-patient basis. This means that even if a patient suffered the same clinical event repeatedly (i.e., events mapped to the same PT) the event will be counted only once and the earliest date will be regarded as start date of the event and the latest date will be regarded as stop date of the event.

#### **4.3.8 Concomitant Medications**

Concomitant medications include all medications and procedures that a patient used at any stage during the study. Any medication started prior to Presentation with attack and used during the study, or medication started at any time after the first study medication administration, thus after Presentation, will be included.

Concomitant medications data was collected throughout the study on the 'Concomitant Medications' CRF page.

Missing concomitant medications data will be handled according to the rules specified in Section 5.5.2.4.

#### **4.3.8.1 Coding of Concomitant Medication Terms**

Concomitant medications are classified according to active drug substance using the World Health Organization Anatomical Therapeutic Chemical (WHO ATC) Index 2015 or later.

The ATC code has 7 characters. The first character gives the anatomical main group (1st level), the first 3 characters give the therapeutic main group (2nd level), the first 4 characters give the therapeutic subgroup (3rd level), the first 5 characters give a further level therapeutic subgroup (4th level), whereas the 7 characters give the subgroup for the chemical substance. In this study, ATC codes are defined to the 4th level.

Although there can be multiple ATC classes for a drug, each drug will be linked with one ATC class which will be assigned manually during the coding process, based on information about the indication and route in relation to the study therapeutic area. This one ATC class will be indicated as the 'primary' ATC class, and only the primary class will be presented.

Coding of CMs will be provided by data management at PSR in a coding spread sheet alongside the coding of AEs and MH. The CM coding data will be merged onto the raw CM data using the variables "Subject ID" and "CM no.". The final version of this spreadsheet will be provided prior to database lock.

#### **4.3.9 Treatment Compliance**

As this study involves i.v. administration of the study medication administered by study personnel, patient compliance measures will not be reported (as detailed in Section 9.7 of the study protocol).

#### **4.3.10 Intercurrent HAE attacks**

Occurrence of intercurrent HAE-episodes will be recorded at Days 28 and 90 after the treated attack and at yearly follow up visits from the Screening visit thereafter.

### **5. Statistical Methodology**

#### **5.1 General Statistical Methods**

##### **5.1.1 General Information**

All analysis data sets and output, with the exception of the PK/PD analyses and output, will be produced by the Biostatistics Department of Quanticate Ltd using the SAS® system Version 9.3 or higher.

##### **5.1.2 Default Descriptive Statistics and Data Rules**

Unless otherwise stated, summary statistics including the number of patients, mean, standard deviation (SD), median, minimum and maximum, will be presented for all continuous variables. Minimum and maximum values will be presented to the same decimal precision as the raw values, the mean and median values to one more, and the SD, to two more decimal places than the raw values.

For categorical variables, per category, the absolute counts (n) and percentages (%) of patients with data, and if appropriate, the number of patients with missing data, will be presented. All percentages will be presented to one decimal place.

For AEs reported on a per-patient basis, medical history and concomitant medications, the denominator for the percentage calculation will be the number of patients. A patient will be considered at risk if the patient is in the Safety/FAS analysis set.

## **5.2 Hypotheses and Decision Rules**

No formal hypothesis testing will be conducted for this study.

## **5.3 Covariates**

There will be no covariates included in analyses.

## **5.4 Multi-Centre Data**

No analyses by center will be conducted.

## **5.5 Handling of Missing Data**

### **5.5.1 Efficacy Endpoints**

For the time to event efficacy endpoints, if there is insufficient data to ascertain whether a patient has had an event, it will be assumed that they have not had the event.

### **5.5.2 Safety Endpoints**

#### **5.5.2.1 Exposure**

If the start of treatment date is missing, the latest possible time of all the pre-dose assessments, will be imputed as the start of treatment date.

#### **5.5.2.2 Adverse Events**

Missing and/or incomplete dates/times for AEs are imputed in a manner resulting in the earliest onset or the longest duration during the treatment period, taking additionally into account that the start date/time should not be after the stop date/time. Stop dates/times will not be imputed if the AE is on-going. This will be done as follows:

For a missing/incomplete start date/time the minimum of the following will be imputed:

- The maximum of the earliest possible start date/time and the date/time of first study medication administration.
- The latest possible start date/time.
- The latest possible stop date/time.

For a missing/incomplete stop date/time the maximum of the following will be imputed:

- The minimum of the latest possible stop date/time and the date/time of last study medication administration.
- The earliest possible stop date/time.
- The earliest possible start date/time.

The earliest (latest) possible date is defined as:

- The date itself if it is complete.
- The date of the first (last) day of the month, if month and year are available but day is missing.
- The date of the first (last) day of the year, if year is available but day and month are missing.
- A very early (late) date, e.g., 01JAN1000 00:00hrs (01JAN3000 23:59hrs), if the date is completely missing.

The imputation method will only be used to determine treatment emergence and to determine the time of the event relative to the first administration of study medication.

A worst-case approach will be followed in the event of missing severity or causality data. If the severity is missing, 'Severe' will be imputed. If causality data is missing, 'Related to study medication' will be imputed.

In the event that no coding information is available for a specific AE, the AE will be presented as an 'Uncodable Event' in summary tables.

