12.3.3 Safety data

The analysis of safety will be performed on the basis of the Safety Set. It will be descriptive and consist of:

Immunogenicity data (anti-C1INH antibodies of IgG and IgM, anti-HRI)

- descriptive statistics at each assessment time (attack/day)
- documented list of all immunology data (including the data of the confirmatory assays), for the patients for whom any value was observed above the cut-off level

Adverse events

AEs will be recorded throughout the study. These will be coded using the MedDRA dictionary, version 13.1 or later. The analysis will be based on the treatment-emergent adverse events (TEAE), which are the AEs with an onset at any time between the start of treatment and 97 days after treatment for any treated attack.

The following documented lists of individual data will be provided for all attacks together:

- documented list of individual data concerning TEAEs
- documented list of baseline adverse events with onset before start of treatment administration for the first attack, and for subsequent, AEs with onset between 98 days since the previous treated attack and the start of treatment administration

The analysis of TEAEs will be performed by attack number and all attacks together. It will consist of:

- frequency distribution of patients with TEAEs, with serious TEAEs, and with TEAEs causing premature discontinuation
- frequency distribution of patients with TEAEs by system organ class
- frequency distribution of patients with TEAEs by system organ class and preferred term
- frequency distribution of patients with related TEAEs by system organ class and preferred term

If relevant:

- frequency distribution of patients with TEAEs by system organ class, preferred term and maximal severity
- frequency distribution of patients with TEAEs by system organ class, preferred term and strongest relationship

HAE attacks

HAE attacks will be separately recorded. The analysis will consist of:

- documented list of individual data concerning HAE attacks

Laboratory data (hematology, biochemistry)

- Descriptive statistics at each assessment time (attack/day).
- For each attack number descriptive statistics of the difference between the recording before treatment and Day 28 (if this visit occurred before the next treatment).
- Frequency distribution of the status (below, within, and above the normal range), at each assessment time.

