#### **4.2.2.1 Adverse Event Definitions**

A treatment-emergent adverse event (TEAE) is defined as an AE that occurred or increased in severity within 97 days of a dose of study medication. If there are partial or missing dates for when the AE started then it will be assumed that the AE was treatment emergent unless it can be determined from the partial start date or stop date that the AE definitely started before the first dose of study medication, or more than 97 days after the patient last received study medication. Tables will include only TEAEs, but all AEs will be listed.

Serious adverse events (SAEs) reported from the time of informed consent until the last follow-up visit (Day 90) after the last dose of study medication will be recorded as part of the study. SAEs will be any AE where the question 'Does the adverse event meet the criteria of serious?' has been answered as 'Yes'.

A treatment-emergent serious adverse event (TESAE) is defined in exactly the same manner as a TEAE, with the exception that the AE in question must be classified as an SAE.

Each AE will be assigned to an attack based on the start date. If the AE starts after study medication was received for Attack N but prior to study medication being received for Attack N+1 then the AE will be assigned to Attack N. If it is not possible to ascertain from the partial date during which attack the AE occurred then the AE will be assigned to the last possible attack based on the partial date.

The time from previous administration of study drug to onset of an AE will be calculated for all TEAEs as follows:

Date/Time of onset of AE – Date/Time of the start of previous administration of study drug.

An AE will be classified as related to study medication if the relationship to study medication was recorded (on the 'Study Adverse Events' CRF page,) as, 'Possible', 'Probable', 'Definite'. An AE will be classified as unrelated to study medication if the relationship to study medication was recorded as 'Unrelated'.

An AE leading to study discontinuation will be defined as an AE where 'Action taken discontinued study drug' is selected on the Adverse Events CRF page and/or '(Serious) Adverse Event experience' is selected as reason for end of study on the End of Study CRF page.

An AE leading to death will be any AE where the outcome is marked as "4 (Death)".

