#### **5.5.2.4 Concomitant Medications**

Missing concomitant medication dates will be handled in a similar fashion as described for AEs in Section 5.5.2.2.

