### 6.8.2 Adverse Events

AEs will be recorded throughout the study. These will be coded using the MedDRA dictionary, version 18.0 or later. Tables will only summarize TEAEs; all AEs will be listed.

TEAEs will be summarized using absolute counts (n) and percentages (%). Summaries will be presented by SOC and PT. Results will be sorted by decreasing frequency of the SOC and PT within the SOC.

AE tables will be presented by attack for the Safety Analysis Set. A separate column will be included summarizing AEs reported regardless of attack number. For the overall column, percentages will be presented out of the total number of patients in the Safety Analysis Set and counting will be by patient, so if a patient has the same AE in more than one attack this will only be counted once in the overall column.

The following tables will be produced:

- Overall summary of Adverse Events
- Incidence of Treatment-Emergent Adverse Events
- Incidence of Related Treatment-Emergent Adverse Events
- Incidence of Treatment-Emergent Adverse Events Commencing Within 24 Hours of the Completion of the Infusion of Study Drug Administration
- Incidence of Treatment-Emergent Adverse Events Commencing Within 28 Days of the Completion of the Infusion of Study Drug Administration
- Incidence of Treatment-Emergent Adverse Events by Strongest Relationship (Investigator's Judgment)
- Incidence of Treatment-Emergent Adverse Events by Maximum Severity (Investigator's Judgment)
- Incidence of Treatment-Emergent Serious Adverse Events
- Incidence of Treatment-Emergent Adverse Events Leading to Study Discontinuation
- Incidence of Treatment-Emergent Adverse Events of Special Interest

The Summary of Adverse Events table will be presented by attack and will show the following:

- Number (%) of Deaths
- Number (%) of Treatment-Emergent Deaths
- Number (%) of Subjects With At Least One SAE
- Number (%) of Subjects With At Least One TESAE
- Number (%) of Subjects Who Prematurely Discontinued the Study Due to a TEAE
- Number (%) of Subjects With At Least One TEAE
- Number (%) of Subjects With At Least One Related TEAE
- Number (%) of Subjects Without Any TEAEs

All AEs will be listed. Listings will include CRF collected data, coded terms (primary SOC and PT) and a flag for treatment emergence. The time from last administration of study drug to onset of an AE (hours) will be listed for TEAEs. Separate listings will be produced for any SAEs and any AEs leading to study discontinuation.

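### The SAP's imputation of incomplete AE start dates/times is anchored to the first study dose only; in repeat attacks it can place an AE before the dose, conflicts with SAP 4.2.2.1, and leaves the 24-hour and 28-day tables without a rule

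*SAP*

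**What the plan says.** SAP 5.5.2.2 imputes an incomplete AE start as the minimum of three values: the latest possible start, the latest possible stop, and "The maximum of the earliest possible start date/time and the date/time of first study medication administration". For the earliest and latest possible values, a complete calendar date is taken as "The date itself if it is complete"; no clock-time convention is given. The same section restricts its use: "The imputation method will only be used to determine treatment emergence and to determine the time of the event relative to the first administration".

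SAP 4.2.2.1 defines a TEAE as "an AE that occurred or increased in severity within 97 days of a dose of study medication". Protocol 12.3.3 fixes the direction of the window: "the AEs with an onset at any time between the start of treatment and 97 days after treatment for any treated attack". SAP 4.2.2.1 also has its own defaults. An AE with a partial or missing start date is presumed treatment-emergent unless it definitely began before the first dose or more than 97 days after study medication was last received. If the partial date leaves the attack uncertain, the last possible attack is used. Otherwise assignment goes by interval: "If the AE starts after study medication was received for Attack N but prior to study medication being received for Attack N+1" means Attack N.

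SAP 6.8.2 presents AE tables by attack, including "Incidence of Treatment-Emergent Adverse Events Commencing Within 24 Hours of the Completion of the Infusion of Study Drug Administration" and a 28-day counterpart. Only TEAEs are tabulated; all AEs are listed. The protocol allows up to 10 treated attacks per patient, at least 24 hours apart (sections 6 and 7.3).

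**The concern.** The start rule suits a single-dose study. Its purpose is to stop an AE with an incomplete onset from falling before treatment, and it does that only for the first dose. From the second treated attack on, the first dose lies in the past and no longer constrains the result.

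Safety is the primary objective, effects after repeat treatment are to be explored (Protocol 10.1.3), and allergic reaction is the only significant clinical risk the protocol names. With a target of at least 20 children, one AE more or less is visible in a by-attack table. The same kind of record should not be handled differently according to attack number, and two programmers reading 4.2.2.1 and 5.5.2.2 should not produce different TEAE counts.

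**Working it through.** The plan gives no figure to reproduce, so the check applies the rule as written.

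**Formula (SAP 5.5.2.2).** Imputed start = min{ max(earliest possible start, first dose), latest possible start, latest possible stop }.

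**Illustrative inputs.** Dose 1 on 10 January 2015 at 14:00; dose 2 a chosen number of days later at 14:00; AE dated on the day of the dose, no clock time, ongoing. Earliest possible time 00:00 and latest 23:59. These times are inferred from the section's example for a wholly missing date.

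**Attack 1.** max(00:00, 14:00) = 14:00, the dose time. The AE is treatment-emergent, as intended.

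**Attack 2.** max(00:00 on the day of dose 2, 10 January 14:00) = 00:00 on the day of dose 2, which is 14 h before that dose at every gap.

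| Days from dose 1 to dose 2 | Imputed onset after dose 1 | TEAE by 5.5.2.2 | By 4.2.2.1, if a missing time counts as partial |
|---|---|---|---|
| 1 | 10 h | yes | TEAE, Attack 2 |
| 20 | 19 d 10 h | yes | TEAE, Attack 2 |
| 60 | 59 d 10 h | yes | TEAE, Attack 2 |
| 97 | 96 d 10 h | yes | TEAE, Attack 2 |
| 98 | 97 d 10 h | no | TEAE, Attack 2 |
| 150 | 149 d 10 h | no | TEAE, Attack 2 |
| 365 | 364 d 10 h | no | TEAE, Attack 2 |

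**Month and year only.** Take the 150-day case: dose 2 is on 9 June 2015 at 14:00 and the AE is dated June 2015. Under 5.5.2.2 the onset is max(1 June, 10 January 14:00) = 1 June. At 00:00 that is 8 d 14 h before dose 2 and 150 d − 8 d 14 h = 141 d 10 h after dose 1, so not treatment-emergent. Under 4.2.2.1 the date is plainly partial and neither exception is met, so the AE is a TEAE of Attack 2. This conflict does not depend on the 00:00 convention: any time on 1 June gives the same result.

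**24-hour and 28-day tables.** They need onset relative to the dose of each attack. The scope sentence in 5.5.2.2 permits the imputed value for treatment emergence and for time relative to the first administration only. For Attack 2 onwards, no permitted value exists. The last-possible-attack rule in 4.2.2.1 settles the attack but not the hours or days since dosing.

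**How often a gap exceeds 97 days (assumption).** If attacks follow a Poisson process and all are treated, P = exp(−rate × 97/365.25): 77% at 1 attack a year, 27% at 5, 20% at 6 and 4% at 12. Protocol 4.1 cites a general HAE series with 31% of patients below 1 a year, 23% at 1 to 5 and 46% at 6 or more; it does not describe this cohort. Gaps over 97 days are therefore realistic. This says nothing about how many AEs lack a time or a day.

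**After the change proposed below.** In all seven same-day cases the floor is dose 2, the imputed onset is 14:00, and the AE is a TEAE of Attack 2 inside both windows. The month-only AE moves to 9 June 14:00, also Attack 2. The Attack 1 case is unchanged.

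**The case against.** The strongest reply is that SAP 4.2.2.1 already protects these events. If a date without a time is partial, every case in the table stays a TEAE of Attack 2. A reader might infer from 5.5.2.2 alone that such AEs are certain to vanish from the TEAE tables. The documents do not support that: the loss needs a gap above 97 days and a reading in which 5.5.2.2 prevails over 4.2.2.1. The SAP settles neither which section prevails nor whether a missing time is partial. What it shows is a conflict, not a certain loss.

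A reader might also infer that the imputed time moves the AE to the previous attack and out of the current attack's 24-hour table. If the value were carried over, the AE would stay in the 24-hour table under Attack 1 at a 1-day gap, leave that table at 20 days, and leave the 28-day table too at 60 days. But the scope sentence does not authorise that use. The defect in those tables is an absent rule, not a rule that displaces events.

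The 00:00 is inferred, and comparison at date level would remove the same-day problem. That stands, but it does not help the month-only case.

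Missing times may be rare. Protocol 11.1.5 requires date and time of onset, the child is observed for 4 hours, and AEs of special interest are reported within 24 hours. Against this, Protocol 11.1.1 asks for start and stop dates on the AE pages, and later AEs come partly from a home diary. Repeat treatments made up 106/168 (63%) to 137/194 (71%) of treatments in the adult-programme extensions, where (168 − 62) = 106 and (194 − 57) = 137. Those are shares of treatments, not of untimed AEs, and do not measure the effect.

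Two extensions fail. SAP 5.5.2.4 says "Missing concomitant medication dates will be handled in a similar fashion as described for AEs in Section 5.5.2.2", which is too loose to show that therapeutic failure would be misclassified. That the acute tables exclude reactions during the injection rests on one narrow reading of their titles.

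**Conclusion.** The concern holds as a defect in a stated rule, not merely as missing detail. SAP 5.5.2.2 says its imputed value determines treatment emergence, and for repeat attacks that value can lie before the dose and outside the 97-day window of the previous one. It then contradicts 4.2.2.1. For dates with month and year only, the contradiction follows from the text; for same-day AEs without a time it also assumes 00:00 as the earliest time. The by-attack 24-hour and 28-day tables have no valid rule for these AEs in either case.

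The size is unknown: the documents do not say how many AEs have an incomplete onset near a repeat dose. A systematic bias in the reported safety results is not shown. All AEs appear in the listings, so affected records can be found. It should be corrected, at moderate priority.

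**What to change.** Make three changes to the SAP text.

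1. In the start rule of 5.5.2.2, replace the first dose as floor with the start of the latest study medication administration on or before the earlier of the latest possible AE start and the latest possible AE stop. If there is none, keep the first administration.
2. State that a missing clock time makes a date partial for the purposes of 4.2.2.1.
3. Extend the scope sentence in 5.5.2.2 so that the same imputed onset serves treatment emergence, attack assignment and the 24-hour and 28-day tables.

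The new floor agrees with the last-possible-attack rule. The cost is a few sentences and a small programming change. The downside is that some untimed events that really began before the dose may be counted as TEAEs, and a month-only AE in a month with a dose may be placed at that dose and so enter the 24-hour table. Both errors are conservative for safety.

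The SOP deviation form attached to the SAP says the analysis is finalised. The practical step is to count AEs with an incomplete onset that could fall on or after a repeat dose, rerun the affected tables if there are any, and describe the change in the CSR, which SAP 7.5 provides for.
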